5 STUDY POPULATION

5.1 INCLUSION CRITERIA

Study entry is open to adults regardless of race or ethnic background. While there will be every effort to seek out and include minority patients from both genders, the patient population is expected to be no different from that of the populations in Minnesota and Kampala, Uganda.

In order to be eligible to participate in this study, an individual must meet all of the following criteria

1. Age ≥ 18 years but < 60 years
2. No contraindication to Yellow Fever vaccine (immunosuppressed for any reason or on an immunosuppressive drug where a live virus vaccine is contraindicated).
3. If female of childbearing age must agree to contraception for one month following administration of the vaccination.

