5.2 EXCLUSION CRITERIA

An individual who meets any of the following criteria will be excluded from participation in this study

1. History of yellow fever or previous vaccination for yellow fever
2. Known bleeding disorder
3. Prior surgery complicated by clotting abnormality
4. Psychiatric or behavioral disorder that, in the opinion of the investigator, will make it difficult for the participant to complete the study
5. History of acute hypersensitivity reaction to any component of the vaccine (including gelatin, eggs, egg products, or chicken protein).
6. Thymus disorder associated with abnormal immune function
7. Immunosuppression from any of the following: HIV infection or AIDS, malignant neoplasms, primary immunodeficiencies, transplantation, transplantation, immunosuppressive or

immunomodulatory therapy (corticosteroids, alkylating agents, antimetabolites, TNF inhibitors, IL-1 blocking agents, monoclonal antibodies targeting immune cells), previous radiation therapy.

8. Pregnant or breastfeeding at the time of vaccination.
9. Planning to conceive within 28 days of enrollment and vaccination with the yellow fever vaccine.

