7.2 PARTICIPANT DISCONTINUATION/WITHDRAWAL FROM THE STUDY

Participants are free to withdraw from participation in the study at any time upon request.

An investigator may discontinue or withdraw a participant from the study for the following reasons:

- Pregnancy within 28 days of vaccination
- Significant study non-compliance
- If any clinical adverse event (AE), laboratory abnormality, or other medical condition or situation occurs such that continued participation in the study would not be in the best interest of the participant

- Acquisition of HIV

The reason for participant discontinuation or withdrawal from the study will be recorded on a Case Report Form (CRF) designed for this purpose. Subjects who sign the informed consent form but do not receive the study intervention may be replaced. Subjects who sign the informed consent form, and receive the study intervention, and subsequently withdraw, or are withdrawn or discontinued from the study, will not be replaced.

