During the COVID-19 pandemic, participants will be screened for COVID-19 symptoms before coming in for their visits. There will also be AE assessments.

Day 17

At Day 17, participants will have a research blood draw of 60 cc. Blood will be collected for yellow fever neutralizing antibody. There will also be an AE assessment. During the COVID-19 pandemic, participants will be screened for COVID-19 symptoms before coming in for their visit.

Week 3

At Week 3, participants will undergo a lymph node biopsy will be stored. Blood will be collected for:

- T cell panel
- Luminex
- PBMC/plasma storage

Females of childbearing potential will have a serum or urine pregnancy test. There will also be an AE assessment. During the COVID-19 pandemic, participants will be screened for COVID-19 symptoms before coming in for their visit.

Weeks 4 through 10

Participants will return every 2 weeks (see SOEs, Sections 1.2 and 1.3) for blood draws for:

- PBMC/plasma storage
- Yellow fever neutralizing antibody (week 8 only)

At Week 4, females of childbearing potential will have a serum or urine pregnancy test. Stool will be collected for microbiome study.

There will also be an AE assessment. During the COVID-19 pandemic, participants will be screened for COVID-19 symptoms before coming in for their visit.

Week 12

Blood will be collected for:

- HIV antibody
- PBMC/plasma storage
- Luminex

Stool and urine will be collected to check for helminths. There will also be an AE assessment. During the COVID-19 pandemic, participants will be screened for COVID-19 symptoms before coming in for their visit.

Months 6 through 15

Participants will return quarterly starting Month 6 through Month 18.

Months 6, 9, 12 and 15 participants will have blood collected for PBMC/plasma storage.

Month 6 will have stool will be collected for microbiome study. During the month 6 timepoint, leukapheresis will be performed. Before leukapheresis, females of childbearing potential will have a serum or urine pregnancy test. If a participant is not eligible or unable to tolerate leukapheresis, a large volume blood draw (60 cc) will be done.

At the month 12 visit, participants will have stool and urine collected for helminth check. Stool will be collected for microbiome study, and blood will be collected for:

- HIV antibody
- Luminex
- PBMC/plasma storage

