8.3.4 TIME PERIOD AND FREQUENCY FOR EVENT ASSESSMENT AND FOLLOW-UP

The occurrence of an adverse event (AE) or serious adverse event (SAE) may come to the attention of study personnel during study visits and interviews of a study participant presenting for medical care, or upon review by a study monitor.

All AEs including local and systemic reactions not meeting the criteria for SAEs will be captured on the appropriate case report form (CRF). Information to be collected includes event description, time of onset, clinician's assessment of severity, relationship to study product (assessed only by those with the training and authority to make a diagnosis), and time of resolution/stabilization of the event. All AEs occurring while on study must be documented appropriately regardless of relationship. All AEs will be followed to adequate resolution.

Any medical condition that is present at the time that the participant is screened will be considered as baseline and not reported as an AE. However, if the study participant's condition deteriorates at any time during the study, it will be recorded as an AE.

Changes in the severity of an AE will be documented to allow an assessment of the duration of the event at each level of severity to be performed. AEs characterized as intermittent require documentation of onset and duration of each episode.

The principal investigator or study staff will record all reportable events with start dates occurring any time after informed consent is obtained until 7 (for non-serious AEs) or 30 days (for SAEs) after the last day of study participation. At each study visit, the investigator will inquire about the occurrence of

AE/SAEs since the last visit. Events will be followed for outcome information until resolution or stabilization.

In Uganda, the sponsor has taken out clinical trials insurance policy to cover compensation for any personal injury resulting from participants taking the study medication and/or study procedures, provided such personal injury is not due to fault or negligence of the study doctor or his team.

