8.3.9 REPORTING OF PREGNANCY

Not applicable.

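### Pregnancy reporting is marked as not applicable in a live-vaccine trial that lists early pregnancy as a withdrawal reason, so nothing requires a withdrawn woman's pregnancy to be followed to outcome

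*Combined protocol and SAP*

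**What the plan says.** Several provisions of the combined protocol and SAP treat roughly the first month after vaccination as a protected period:

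- Section 5.1: "If female of childbearing age must agree to contraception for one month following administration of the vaccination".
- Section 5.2 excludes a woman who is "Planning to conceive within 28 days of enrollment and vaccination with the yellow fever vaccine".
- Section 7.2 lists "Pregnancy within 28 days of vaccination" among the reasons for which an investigator may withdraw a participant. The reason for withdrawal goes on a case report form (CRF).

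Section 8.2 plans pregnancy tests after vaccination on Days 7 and 14 and at Week 3. Then: "At Week 4, females of childbearing potential will have a serum or urine pregnancy test". The next test in that text is at Month 6: "Before leukapheresis, females of childbearing potential will have a serum or urine pregnancy test". For a woman who does not have the procedure: "If a participant is not eligible or unable to tolerate leukapheresis, a large volume blood draw (60 cc) will be done". No test is stated there for that route.

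The section headed "8.3.9 REPORTING OF PREGNANCY" contains only the statement that it is not applicable.

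On safety capture, section 8.3.2 counts a congenital anomaly as serious. Under section 8.3.4, "At each study visit, the investigator will inquire about the occurrence of" adverse and serious adverse events, and SAE recording closes 30 days after the last day of participation. Under section 10.1.5, both Independent Safety Monitors (ISMs) are told of SAEs and can see participant records.

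**The concern.** The protocol makes pregnancy soon after a live vaccine an event on which the investigator may act, and it tests for that event. It then declares pregnancy reporting not applicable. This is a stated rule rather than a silence. Followed literally, nobody has to notify the ISMs of an exposed pregnancy or learn how it ended.

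The action that 7.2 offers makes this worse. Withdrawal starts the 30-day clock on SAE recording, so it can close the one route by which a congenital anomaly would be captured. At stake are the counselling of the participant and knowledge of the outcome of an exposed pregnancy. No efficacy result is at stake.

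A smaller, secondary question is whether the test schedule reaches the end of the 28 days.

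**Working it through.** The plan gives no figure of its own on this point, so there is none to reproduce. The check is calendar arithmetic on the stated visits.

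**Inputs from the documents.** Women: 15 in Uganda and 8 in Minnesota (4.1), 23 in all, fewer once limited to those of childbearing potential. Visit windows (1.3): Weeks 4, 6 and 8 are each +/- 3 days; Month 6 is +/- 14 days. SAE recording ends 30 days after last participation (8.3.4).

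**Assumptions, not in the documents.** Conception to birth: 37 to 39 weeks (259 to 273 days). Lag from conception to a positive test: 8 to 14 days. Pregnancy rate: 1% to 10% per woman-year. One month is 30.44 days. Week 4 is taken as Day 28 and the window as ending on Day 28. If both are counted from a Day 1 vaccination they move together to Day 29, and the shortfalls below do not change. The day of withdrawal is taken as the last day of participation.

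**1. A woman withdrawn under 7.2.** Take withdrawal at Week 8 (Days 53 to 59) and conception on Day 28.

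- SAE recording ends: 53 + 30 = Day 83 to 59 + 30 = Day 89.
- Birth: 28 + 259 = Day 287 to 28 + 273 = Day 301.
- Gap: 287 - 89 = 198 to 301 - 83 = 218 days.

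The choice of Week 8 matters little. For a birth on Day 287, any withdrawal before 287 - 30 = Day 257 closes SAE recording before the birth.

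**2. A woman who stays in.** Birth on Days 287 to 301 comes before Month 12 (12 x 30.44 = Day 365) and well before Month 18, so a congenital anomaly present at birth would be recorded as an SAE. The gap in outcome capture is therefore sharpest for the withdrawn woman.

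**3. Test timing (secondary).** The Week 4 visit may fall on Days 25 to 31.

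- With no lag, shortfall = max(0, 28 - visit day). Days 25, 26 and 27 give 3, 2 and 1 days; Days 28 to 31 give 0.
- If 7.2 refers to conception and there is a lag, unseen days = max(0, 28 - (visit day - lag)):

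| Week 4 visit | lag 0 | lag 8 | lag 14 |
|---|---|---|---|
| Day 25 | 3 | 11 | 17 |
| Day 28 | 0 | 8 | 14 |
| Day 31 | 0 | 5 | 11 |

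- Wait to the next test in 8.2 after a Day 28 conception: 6 x 30.44 - 28 = 155 days, or 141 to 169 with the Month 6 window.

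**4. Expected number of unseen conceptions** = 23 x annual rate x unseen days / 365.

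- Low: 23 x 0.01 x 5 / 365 = 0.003.
- High: 23 x 0.10 x 17 / 365 = 0.107, about 0.11.

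The high value takes all 23 women as being of childbearing potential, every Week 4 visit on its earliest day, the longest lag, and the top rate despite agreed contraception. Neither value allows for pregnancies that come to light at the Week 6, 8, 10 and 12 visits.

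**5. What one more test would cover.** Largest lag with full coverage = earliest visit day - 28. Week 6: 39 - 28 = 11 days. Week 8: 53 - 28 = 25 days.

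**The case against.** The other side has a fair case. Four pregnancy tests within about a month of a licensed vaccine at its standard dose is a defensible schedule in a 46-person study. The dose cannot be undone, withdrawal is discretionary, and entry requires contraception. A pregnancy is not invisible either: it can be raised when adverse events are asked about, a withdrawal reason goes on a CRF, and the ISMs have ongoing access to records. Counselling may be covered in the consent form, the vaccine SOP or the manual of procedures, none of which can be seen here.

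Most of this stands against the test-timing half. Section 7.2 does not say whether it means a pregnancy conceived or one detected within 28 days. Under the second reading, only a Week 4 visit on Days 25 to 27 falls short. The 5-to-17-day figures need both the conception reading and an assumed lag. The 60 cc point rests on 8.2 alone. The late pregnancy-test mark in the 1.3 table is limited only to females of childbearing potential, and its column is uncertain in the extracted table.

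It does not answer the 8.3.9 half. A CRF withdrawal reason records that a pregnancy led to withdrawal, not how it ended. ISM access permits someone to notice a pregnancy but obliges nobody to report it. Section 8.3.4 follows adverse events to resolution or stabilization, but 8.3.1 defines these as untoward occurrences and nothing classes pregnancy itself as one. Unseen documents may add counselling, but they would sit beside a protocol section that says pregnancy reporting does not apply.

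**Conclusion.** The concern holds for section 8.3.9. Marking pregnancy reporting as not applicable is at odds with 5.1, 5.2, 7.2 and 8.2, and for a withdrawn woman SAE recording would close roughly 200 days before birth. That figure rests on the assumed time from conception to birth and on withdrawal at about Week 8; its direction does not. The matter is minor, worth considering rather than essential: at most 23 women, and a rare event.

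The test-timing observation is secondary and optional. It is firm only to the extent of up to 3 days for an early Week 4 visit. Beyond that it depends on a lag that the documents do not give.

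A reader might infer three stronger things, and the documents support none of them:

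- *That the schedule fails a requirement to detect every conception up to Day 28.* No section sets that requirement.
- *That late-window pregnancies will generally go unnoticed until Month 6.* Adverse event inquiry at Weeks 6 to 12 can surface any pregnancy the woman knows of and reports. The expected number of unseen conceptions is about 0.003 to 0.11 even before allowing for this.
- *That the primary result is at risk.* The peak-titer comparison does not depend on any of this.

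**What to change.** **Main change.** Replace the entry in 8.3.9 with: *A pregnancy conceived within 28 days of vaccination is recorded, the participant is counselled, both ISMs are informed, and the pregnancy is followed to outcome, including after withdrawal under 7.2.* The cost is a minor amendment. A woman who stays in the study needs no added visit; one who is withdrawn needs a follow-up contact.

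**Optional change.** Add one urine pregnancy test for females of childbearing potential at the existing Week 6 or Week 8 visit, in both 8.2 and 1.3. Week 6 detects sooner but, at its earliest day, covers the whole window only for lags up to 11 days. Week 8 covers lags up to 25 days but detects later. The cost is at most 23 inexpensive tests and one schedule entry.

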7.3 LOST TO FOLLOW-UP

A participant will be considered lost to follow-up if he or she fails to return for scheduled visits and is unable to be contacted by the study site staff.

The following actions must be taken if a participant fails to return to the clinic for a required study visit:

- The site will attempt to contact the participant and reschedule the missed visit and counsel the participant on the importance of maintaining the assigned visit schedule and ascertain if the participant wishes to and/or should continue in the study.
- Before a participant is deemed lost to follow-up, the investigator or designee will make every effort to regain contact with the participant (where possible, 3 telephone calls and, if necessary, a certified letter to the participant's last known mailing address or local equivalent methods). These contact attempts should be documented in the participant's study file.
- Should the participant continue to be unreachable, he or she will be considered to have withdrawn from the study with a primary reason of lost to follow-up.

8 STUDY ASSESSMENTS AND PROCEDURES

8.1 EFFICACY ASSESSMENTS

This study does not contain a therapeutic intervention and therefore there are no efficacy assessments.

8.2 SAFETY AND OTHER ASSESSMENTS

Screening Procedures (Day -42 to 1)

Participants will be consented by the investigator or qualified study staff before any procedures take place.

The following screening blood tests will be obtained:

- CBCD
- Chemistry Panel (including Albumin, ALT, AST, Alk. Phosphate, Bilirubin (total), Calcium, Chloride, CO₂, Creatinine, Glucose, Potassium, Protein (total), Sodium, Urea Nitrogen)
- T Cell Panel
- PT/PTT
- HIV antibody
- Yellow Fever Neutralizing Antibody
- PBMC/Plasma storage (to screen for yellow fever)

We will obtain a detailed medical history to ascertain that potential subjects have not had yellow fever, been vaccinated for yellow fever, and have no history of thymus disease. Females of childbearing

potential will have a serum or urine pregnancy test. During the COVID-19 pandemic, participants will be screened for COVID-19 symptoms before coming in for their visit.

Baseline Procedures (Day -35 to 1)

Medical history and concurrent medications ascertained. Physical examination and vital signs, including blood pressure, pulse and weight will be conducted. There will also be an AE assessment. Leukapheresis will be performed. Before Leukapheresis, females of childbearing potential will have a serum or urine pregnancy test. If a participant is not eligible for leukapheresis based on the apheresis consultation appointment or is unable to tolerate leukapheresis, a large volume blood draw (60 cc) will be done instead. Participants will undergo a lymph node biopsy tissue will be stored. Participants will have stool and urine collected for a helminth check. Stool will be collected for microbiome study.

Blood will be collected for:

- T cell panel
- Luminex
- PBMC/plasma storage

During the COVID-19 pandemic, participants will be screened for COVID-19 symptoms before coming in for their visits.

Day 1

Yellow fever vaccine will be administered. During the COVID-19 pandemic, participants will follow the travel clinics' procedures for screening of COVID-19 symptoms before coming in for their visit.

Days 3 through 14

Participants will return every 2 to 3 days (see SOEs, Sections 1.2 and 1.3) for blood collection for:

- PBMC/plasma storage
- Yellow fever neutralizing antibody

Stool will be collected on Day 10 for microbiome study.

On Days 7 and 14, females of childbearing potential will have a serum or urine pregnancy test.

During the COVID-19 pandemic, participants will be screened for COVID-19 symptoms before coming in for their visits. There will also be AE assessments.

Day 17

At Day 17, participants will have a research blood draw of 60 cc. Blood will be collected for yellow fever neutralizing antibody. There will also be an AE assessment. During the COVID-19 pandemic, participants will be screened for COVID-19 symptoms before coming in for their visit.

Week 3

At Week 3, participants will undergo a lymph node biopsy will be stored. Blood will be collected for:

- T cell panel
- Luminex
- PBMC/plasma storage

Females of childbearing potential will have a serum or urine pregnancy test. There will also be an AE assessment. During the COVID-19 pandemic, participants will be screened for COVID-19 symptoms before coming in for their visit.

Weeks 4 through 10

Participants will return every 2 weeks (see SOEs, Sections 1.2 and 1.3) for blood draws for:

- PBMC/plasma storage
- Yellow fever neutralizing antibody (week 8 only)

At Week 4, females of childbearing potential will have a serum or urine pregnancy test. Stool will be collected for microbiome study.

There will also be an AE assessment. During the COVID-19 pandemic, participants will be screened for COVID-19 symptoms before coming in for their visit.

Week 12

Blood will be collected for:

- HIV antibody
- PBMC/plasma storage
- Luminex

Stool and urine will be collected to check for helminths. There will also be an AE assessment. During the COVID-19 pandemic, participants will be screened for COVID-19 symptoms before coming in for their visit.

Months 6 through 15

Participants will return quarterly starting Month 6 through Month 18.

Months 6, 9, 12 and 15 participants will have blood collected for PBMC/plasma storage.

Month 6 will have stool will be collected for microbiome study. During the month 6 timepoint, leukapheresis will be performed. Before leukapheresis, females of childbearing potential will have a serum or urine pregnancy test. If a participant is not eligible or unable to tolerate leukapheresis, a large volume blood draw (60 cc) will be done.

At the month 12 visit, participants will have stool and urine collected for helminth check. Stool will be collected for microbiome study, and blood will be collected for:

- HIV antibody
- Luminex
- PBMC/plasma storage

There will also be an AE assessment. During the COVID-19 pandemic, participants will be screened for COVID-19 symptoms before coming in for their visit.

Month 18

The month 18 visit will be the final study visit. Stool and urine will be collected for helminth check. Stool will be collected for microbiome study. Blood will be collected for:

- T cell panel
- HIV antibody
- Yellow fever neutralizing antibody
- Luminex
- PBMC/plasma storage

There will also be an AE assessment. During the COVID-19 pandemic, participants will be screened for COVID-19 symptoms before coming in for their visit.

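### Pregnancy at vaccination is an exclusion, but no pregnancy test is scheduled on Day 1, so the last one may be up to about 35 days old when the live vaccine is given

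*Combined protocol and SAP*

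**What the plan says.** Section 1.1 describes the vaccine as live-attenuated. Exclusion 8 in Section 5.2 reads "Pregnant or breastfeeding at the time of vaccination". Exclusion 9 reads "Planning to conceive within 28 days of enrollment and vaccination with the yellow fever vaccine". Inclusion 3 in Section 5.1 reads "If female of childbearing age must agree to contraception for one month following administration of the vaccination". Section 7.2 lists pregnancy in the 28 days after vaccination among the reasons for which an investigator may withdraw a participant, and says that participants withdrawn after vaccination are not replaced.

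Section 8.2 places pregnancy tests for females of childbearing potential at these visits:

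- screening (Day -42 to 1);
- baseline (Day -35 to 1): "Before Leukapheresis, females of childbearing potential will have a serum or urine pregnancy test";
- two early follow-up days: "On Days 7 and 14, females of childbearing potential will have a serum or urine pregnancy test";
- Week 3: "Females of childbearing potential will have a serum or urine pregnancy test. There will also be an AE assessment";
- Week 4: "At Week 4, females of childbearing potential will have a serum or urine pregnancy test";
- Month 6, before the second leukapheresis.

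The Day 1 paragraph provides: "Yellow fever vaccine will be administered. During the COVID-19 pandemic, participants will follow the travel clinics' procedures for screening of COVID-19 symptoms". It does not mention a pregnancy test.

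**The concern.** The exclusion is defined by a woman's status on Day 1, but the plan states no check of that status on Day 1. The last scheduled check is attached to leukapheresis at baseline, a visit that may fall several weeks earlier. The tests that follow the injection can detect an exposed pregnancy but cannot prevent one.

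What is at stake is giving a live vaccine to a participant whom the protocol means to exclude. Section 8.3.9 marks pregnancy reporting as not applicable, so that section gives no reporting step if such an exposure is found. A smaller consequence is that a woman withdrawn on this ground after vaccination would not be replaced, although withdrawal is at the investigator's discretion.

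**Working it through.** The plan gives no figure of its own to reproduce here. The check is a comparison of the text with the Schedule, followed by day arithmetic on the stated windows.

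**1. Is a Day 1 test stated anywhere?** Section 8.2 states seven tests: screening, baseline, Day 7, Day 14, Week 3, Week 4 and Month 6. The pregnancy-test row of the Schedule (Section 1.3) has 21 cells for 21 visit columns and seven marks. As read from the text copy, the marks fall at:

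| Source | 1 | 2 | 3 | 4 | 5 | 6 | 7 |
|---|---|---|---|---|---|---|---|
| Section 8.2 | Screening | Baseline | Day 7 | Day 14 | Week 3 | Week 4 | Month 6 |
| Schedule row | Screening | Baseline | Day 5 | Day 12 | Week 3 | Week 4 | Month 9 |

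Three marks differ in position. That looks like columns shifting when the table was converted to text, and it is not counted against the plan. The numbers agree, seven and seven, so no mark is left over for Day 1. The Day 1 cell is blank.

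**2. Age of the last scheduled test at injection.** The baseline window is Day -35 to Day 1 and the vaccine is given on Day 1.

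- Minimum: baseline done on Day 1, so 0 days.
- Maximum: from Day -35 to Day 1 is 35 days if there is no Day 0, and 1 - (-35) = 36 days if there is.

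Section 8.2 ties the baseline test to leukapheresis, which some participants will not undergo. If the test were omitted for them, only the screening test would remain, at most 42 days old (43 with a Day 0). The Schedule marks the baseline test without that condition, so about 35 days is the fair upper bound.

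**3. Time to the next test.** Day 7 has a window of 1 day either side, so Day 6 to Day 8. Measured from Day 1, that is 6 - 1 = 5 to 8 - 1 = 7 days.

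**4. Do the other criteria cover the interval?** Inclusion 3 starts contraception at vaccination. Exclusion 9 concerns intention to conceive. Neither excludes an unplanned conception between the baseline test and Day 1. No section sets a maximum test age, requires baseline to fall on Day 1, or asks for a repeat test.

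**5. Who is concerned.** Section 4.1 plans 15 women in Uganda and 8 in Minnesota: 15 + 8 = 23 of 30 + 16 = 46. The age range is 18 to under 60, so those of childbearing potential may be fewer.

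**6. Illustration only.** The documents give no conception rate. Assume a chance p per woman of an unplanned conception in the gap. The chance of at least one among n women is 1 - (1 - p)^n.

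| p (assumed) | n = 10 | n = 23 |
|---|---|---|
| 0.2% | 1 - 0.998^10 = 2.0% | 1 - 0.998^23 = 4.5% |
| 2% | 1 - 0.98^10 = 18.3% | 1 - 0.98^23 = 37.2% |

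These figures need a gap of some length; with a same-day baseline, p is close to 0. They count all conceptions in the gap, not only those that a Day 1 test would detect. The conclusion does not rest on them.

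**The case against.** The strongest reply is that silence in one paragraph proves little. The Day 1 paragraph is plainly not a full list: the Schedule marks an adverse event assessment at every visit from baseline on, and the paragraph omits that too. The Schedule row is an imperfect witness, because three of its seven marks disagree with the text. In Minnesota, Section 6.2.1 has the vaccine given under a study SOP at an authorized travel clinic, and a same-day check could well sit there. For Uganda, Section 6.2.1 points to the background account, a results narrative that would not be expected to list pregnancy checks. That account speaks of vaccinating opposite a thigh that had just been biopsied, which suggests a short interval. Exclusion 8 also binds whatever the test date, and two tests precede the vaccine.

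Some of this stands. A Minnesota test may exist, 35 days is a worst case rather than a typical gap, and the assumed conception rates have no source in the plan. None of it supplies a stated check. The SOP is not among the documents. The background account in Section 2.2 gives the injection site and mentions no pregnancy test; a short stretch of that section was not available for this check. An exclusion with no dated test depends on what the participant knows on the day.

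**Conclusion.** The concern holds. As written, the plan makes pregnancy at vaccination an exclusion but states no test on the day of vaccination. The last scheduled test may be 0 to about 35 days old, and the next falls 5 to 7 days after the injection. At most 23 women are affected, 15 of them in Uganda, where the documents point to no other procedure that would include a test.

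This rests on two things: the seven tests in Section 8.2 and the seven Schedule marks being the complete list, and the Minnesota SOP being unseen. If that SOP already requires a test, the Minnesota part becomes a missing cross-reference and the Uganda part remains. The likely number of exposures cannot be derived from the documents. The change should be made for participant safety; the primary comparison, power and analysis are not affected.

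**What to change.** - In Section 8.2 and in the Schedule of Activities, require a negative urine or serum pregnancy test before the injection on Day 1 for every female of childbearing potential at both sites. The maximum age of the last test then falls from about 35 days to 0.
- Start the contraception agreement in inclusion 3 at baseline, because a same-day test can miss a very early conception.
- If the Minnesota vaccine administration SOP already requires the test, cite it in Section 8.2 and apply the same step in Uganda.

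The cost is at most 23 extra tests of a kind the protocol already uses. In Uganda the vaccine is given in the research clinic, so the test can be done there. In Minnesota it has to be arranged with each travel clinic used, or done the same day at the research unit, which may mean an extra attendance. Sample size and analysis stay as they are.
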